## ASSESSMENTS

### Primary Assessment Instrument

- The THINC-it comprised of: Spotter, Symbol Check, Codebreaker, Trails, and PDQ-5-D
- The National Adult Reading Test (NART)

### Secondary Assessment Instruments

- Montgomery Åsberg Depression Rating Scale (MADRS)
- Clinical Global Impression - Severity and Improvement (CGI-S/CGI-I)
- Columbia Suicide Severity Rating Scale (C-SSRS)
- Pen and paper Version of Digit Symbol Substitution Test (DSST)
- Pen and paper Version of the Trail Making Test B (TMT-B)
- Pen and paper Version of the Perceived Deficits Questionnaire for Depression (PDQ-5-D)

- Endicott Workplace Productivity Scale (EWPS)
- Sheehan Disability Scale (SDS)
- WHO-5 Well-Being Index (WHO-5)
- Snaith-Hamilton Pleasure Scale Questionnaire (SHAPS)
- International Physical Activity Questionnaire (IPAQ)
- Generalized Anxiety Disorder Assessment (GAD-7)
  
- THINC-it Satisfaction Questionnaire
  
- 36-Item Short Form Survey Instrument (SF-36)
  
- Insomnia Severity Index (ISI)
  
- Pittsburgh Sleep Quality Index (PSQI)
  
- Epworth Sleepiness Scale (ESS)
  
- Effort Expenditure for Rewards Task (EEfRT) - optional
  
- Changes in blood biomarkers (e.g. BDNF, cytokines, insulin etc.)

Data will be collected using paper based scales that will be administered by the rater or self-reported by the participant.

## **RATIONALE FOR SECONDARY ASSESSMENTS INSTRUMENTS**

A critical question for addressing cognitive impairments in adults with MDD is not whether it exists, but rather determining whether these observed impairments in cognitive function/performance influence patient-reported, clinician-measured, and/or societally defined health outcomes. The answer to which additional testable hypotheses can be generated is to further investigate to what extent cognitive impairments affect these health outcomes and what methods of treatment are available to mitigate these cognitive symptoms. The pen and paper version of the DSST and PDQ-5-D will be administered as an additional measure of validity. Additionally, most individuals achieving remission continue to report/exhibit ongoing functional difficulties as well as significant reductions in quality of life, providing impetus for their measurement [14,15]. Consequently, the WHO-5 will be administered to assess overall quality of life and wellbeing.

Moreover, these deficiencies correlate with greater illness burden measures and costs, particularly in the workplace [16]. Likewise, it is recognized that cognitive function in adults with MDD represents a principal determinant of broad-based psychosocial function [15,17,18]. Taken together, the SDS and EWPS will be administered to allow for secondary evaluation of the relationship between global functional impairment/disability and health-related work productivity with cognitive function in adults with MDD, respectively. It has been amply documented that impairments in cognitive function are correlated with, but dissociable from, depressive symptom severity [18]. Hence, the relationship between measures of cognitive impairment and depressive symptoms severity will include the following secondary measures: the MADRS, the CGI-S/CGI-I, and the CSSRS.

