***Exclusion Criteria for Participants with MDD:***

1. Current alcohol and/or substance use disorder as confirmed by the M.I.N.I 5.0.
2. Presence of comorbid psychiatric disorder other than MDD that is a focus of clinical concern as confirmed by the M.I.N.I 5.0.
3. Medications approved and/or employed off-label for cognitive dysfunction

(e.g., psychostimulants).

4. Any medication for a general medical disorder that, in the opinion of the investigator, may affect cognitive function.
5. Use of benzodiazepines within 12 hours of cognitive assessments.
6. Consumption of alcohol within 8 hours of cognitive assessments.7 . Inconsistent use or abuse of marijuana.
8. Physical, cognitive, or language impairments sufficient to adversely affect data derived from cognitive assessments.
9. Diagnosed reading disability or dyslexia.
10. Clinically significant learning disorder by history.
11. Electroconvulsive therapy (ECT) in the last 6 months.
12. History of moderate or severe head trauma (e.g., loss of consciousness for >1 hour), other neurological disorders, or unstable systemic medical diseases that in the opinion of the investigator are likely to affect the central nervous system.
13. Pregnant and/or breastfeeding.
14. Received investigational agents as part of a separate study within 30 days of the screening visit.
15. Actively suicidal/presence of suicidal ideation or evaluated as being a suicide risk (as per clinical judgment using the Columbia-Suicide Severity Rating Scale).
16. Currently receiving treatment with Monoamine Oxidase Inhibitors (MAOIs) anti-depressants, antibiotics such as linezolid, or intravenous methylene blue.
17. Previous hypersensitivity reaction to vortioxetine or any components of the formulation.  
Angioedema has been reported in patients treated with vortioxetine.
18. Clinical worsening symptoms of depression and suicide risk – in both adult and pediatric age groups.
19. Serotonin syndrome
20. Abnormal bleeding

21. Previous history of mania/hypomania
22. Angle closure glaucoma
23. Hyponatremia
24. Moderate hepatic impairment
25. History of seizures and epilepsy

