### ***Visit 2 (Day 0: Week 0; Baseline)***

Participant will be asked to report any adverse event(s) or any changes to medications. The Clinical Global Impression – Severity (CGI-S), MADRS, as well as the CSSRS scales will be used as part of participant assessment. Anthropometrics (including weight and waist circumference), resting heart rate and blood pressure will be measured. History of caffeine, alcohol, nicotine, exercise and marijuana use will be recorded as well. Participants will be provided with an opportunity to work through the modified THINC-it to minimize potential practice effects with a research team member. This will allow the participant with an opportunity to ask any outstanding questions. The THINC-it tool will be administered via tablet to evaluate objective and subjective measures of cognitive function. THINC-it tests will be consistently delivered in the following order: Spotter, Symbol Check, Codebreaker, Trails, and PDQ-5-D to all participants with a member of the research team instructing participants to read the tutorial

instructions preceding each of the THINC-it tasks. Participants will complete the pen-and-paper version of the Digit Symbol Substitution Test (DSST) and the Trail Making Test B (TMT-B).

Participants will also complete all secondary self-report assessments using paper-based scales/questionnaires and consist of the following scales: Endicott Workplace Productivity Scale (EWPS), Sheehan Disability Scale (SDS), Wellbeing Index (WHO-5), Snaith-Hamilton Pleasure Scale (SHAPS), Generalized Anxiety Disorder (GAD-7), Perceived Deficits Questionnaire for Depression (PDQ-5-D), International Physical Activity Questionnaire (IPAQ), 36-Item Short Form Survey Instrument (SF-36), Insomnia Severity Index (ISI), Pittsburgh Sleep Quality Index (PSQI), Epworth Sleepiness Scale (ESS) and THINC-it satisfaction questionnaire. All self reports will be administered by a member. All study procedures will take place in a quiet setting. Fasting (12-hours) clinical and research bloodwork will also be collected.

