## **Side effects**

Most Common:

- Gastrointestinal adverse events; including nausea, vomiting, constipation/diarrhea. Highest incidence occurs during the first week of treatment. 21-32%
- Sexual dysfunction 14-34%

Less Common: 1-10%

- Dry mouth
- Dyspepsia (discomfort of the abdomen)
- Dizziness
- Somnolence/sedation
- Fatigue
- Insomnia
- Abnormal dreams
- Hyperhidrosis (increase sweating)
- Arthralgia (joint pain)
- Decreased appetite

Rare: %10>

- Nervous system disorders
  - Skin and subcutaneous tissue disorders
  - Psychiatric disorders
- 
- Serotonin Syndrome has been reported with serotonergic anti-depressants (SSRIs, SNRIs, and others), including with Vortioxetine both when taken alone, but especially when coadministered with other serotonergic agents (including triptans, tricyclic antidepressants, fentanyl, lithium, tramadol, tryptophan, buspirone, and St. John's Wort).
  - Treatment with serotonergic antidepressants (SSRIs, SNRIs, and others) may increase the risk of abnormal bleeding. Patients should be cautioned about the increased risk of bleeding when Vortioxetine is coadministered with nonsteroidal anti-inflammatory drugs (NSAIDs), aspirin, or other drugs that affect coagulation.
  - Activation of Mania/Hypomania can occur with antidepressant treatment.
  - Angle Closure Glaucoma: Angle closure glaucoma has occurred in patients with untreated anatomically narrow angles treated with antidepressants.
  - Hyponatremia can occur in association with the syndrome of inappropriate antidiuretic hormone secretion (SIADH).

Please see product monograph for full details.

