## **CONDITIONS FOR WITHDRAWAL FROM THE STUDY**

Participants may discontinue from the study treatment and assessments at any time. Specific reasons for discontinuing a participant from this study are:

1. Voluntary discontinuation by the participant at any time without prejudice to further treatment.
2. Non-compliance to the protocol as judged by the investigator.
3. Participant becomes pregnant.
4. Increased risk of suicide ideation.
5. Any adverse event that, in the opinion of an investigator, puts the subject at risk.

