## STATISTICAL PLAN

Extant literature indicates that the effect size for cognitive deficits in first- and multiple-episode MDD patients is approximately 0.3-0.7 (Cohen's *d*). Notwithstanding the range of reported effect sizes, a modal estimate of 0.4 is instantiated by meta-analyses across disparate domains [23]. Based on an effect size of 0.4, it is estimated that a sample size of 110 evaluable subjects would be required (with a power level of 0.8 and a probability level of 0.05). Similarly, results from our recently completed validation study of the THINC-it demonstrated- temporal reliability of 0.7-0.8, suggesting that repeat-measure performance on the THINC-it between visits would be consistent in the study being proposed herein. Taken together, performance on all the THINC-it tool metrics will be collected in the healthy control group (N=50) for comparison with performance of patients with MDD treated with vortioxetine over an 8-week period, flexibly dosed 10-20 mg/day as adjudicated by a research clinician, to assess detectable differences between groups.

Participants with complete data from the 8 weeks of treatment will be included in analyses, which will be carried out using the Statistical Package for the Social Sciences (SPSS) software. The data will be preliminarily examined in exploratory analyses to obtain their distributional properties, examine any outlying data points, and explore bivariate relations between individual variables. Specific data analyses are subject to change based on the foregoing analyses, but in general we will set  $\alpha = 0.05$ , two-tailed, and  $\beta = 0.20$ .

Validation assessments will be employed based on previous psychometric validations of cognitive assessment, as reported by Harrison et al. (2007) wherein validation was informed by guidance regarding objective psychometric assessment by Ferris et al. (1997) stressing the importance of characterizing the reliability, validity, and sensitivity of cognitive measures; in addition, results from a recently completed validation study of the THINC-it completed by the BCDF will be used to determine the appropriate statistical measures required to perform the study herein.

An important consideration when determining issues such as temporal (or 'test-retest') reliability

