## Test Sensitivity

Performance on the primary metric for each THINC-it tool test will be calculated to determine test sensitivity. Descriptive statistics for performance of i) the Healthy Control group and ii) that of the patients with MDD treated with vortioxetine over 8 weeks will be examined to determine:

- Mean difference in performance on each test
- Variance in performance for each test
- Additional measure of central tendency and variability
- Other descriptions of the data, including skewness and kurtosis
- Mean difference in group performance, characterised as a standardised effect size

Inferential statistical analysis will be conducted to determine significant difference in

performance within and between the two groups. An analysis of the sensitivity (true positive rate) and specificity (the true negative rate) of each test to the presence and subsequent improvement of cognitive impairment in patients with MDD will be conducted. Cut-off models designed to maximize sensitivity and specificity will be evaluated. The model will be optimized to obtain a pragmatic cut-off that maximizes the model with respect to levels of both sensitivity and specificity. In the event that no overlap is apparent, a threshold for determining impairment will be established. Secondary objectives will be addressed with correlative analysis between the total THINC-it tool and/or its components and the disparate secondary measures.

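### The only stated analysis set is 8-week completers and no safety analysis is defined, so participants withdrawn for suicidality or an adverse event fall outside every stated analysis, including that of the C-SSRS

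*Combined protocol and SAP*

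**What the plan says.** **Use of the C-SSRS.** Rationale for Secondary Assessments Instruments groups the scale with the depression ratings: "the relationship between measures of cognitive impairment and depressive symptoms severity will include the following secondary measures: the MADRS, the CGI-S/CGI-I, and the CSSRS". Under Test Sensitivity, the general method is correlation: "Secondary objectives will be addressed with correlative analysis between the total THINC-it tool and/or its components and the disparate secondary measures". Outside analysis, the scale supports the suicidality exclusion ("as per clinical judgment using the Columbia-Suicide Severity Rating Scale") and clinical assessment (for example at Visit 2: "MADRS, as well as the CSSRS scales will be used as part of participant assessment"). The MDD summary chart marks it at all five visits.

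**Analysis set.** Statistical Plan: "Participants with complete data from the 8 weeks of treatment will be included in analyses". The sentence carries no qualification, and no other set is named.

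**Entry and withdrawal.** MDD exclusion 15 keeps out patients who are "Actively suicidal/presence of suicidal ideation or evaluated as being a suicide risk". Conditions for Withdrawal lists "Increased risk of suicide ideation" (item 4) and any adverse event that the investigator considers puts the participant at risk (item 5).

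**Adverse events.** Recordings of Adverse Events requires every event to be recorded, related or not, including whether it led to stopping the product. Serious events are defined for any study phase and go to the regulators. Side Effects gives expected frequencies, among them "Gastrointestinal adverse events; including nausea, vomiting, constipation/diarrhea. Highest incidence occurs during the first week of treatment. 21-32" per cent.

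**Not stated.** The Statistical Plan, including Test Sensitivity, contains no summary of adverse events, serious events, discontinuations or C-SSRS outcomes.

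**The concern.** Taken one at a time, these passages look harmless. Together, they mean that two of the listed reasons for leaving the study are themselves safety outcomes, and that leaving the study removes a participant from the only set the plan defines. Inclusion in the analysis therefore depends on the outcome.

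About 100 depressed patients receive open-label vortioxetine. The natural safety questions are how many developed or worsened in suicidal ideation or behaviour, and how many stopped because of an adverse event. A completer set cannot answer either for those withdrawn. A correlation between the C-SSRS and THINC-it does not answer the first question in any set, because it measures association with cognition and not emergence on treatment.

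That correlation is also weakened. The entry exclusion and the withdrawal condition both tend to remove high C-SSRS scores, which narrows the range left for it.

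**Working it through.** **Plan's own figure.** The plan states no safety rate, safety sample size or safety precision, so there is none to reproduce. Its 110 evaluable subjects concern cognition and do not bear on this point.

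**Inputs from the documents**
- MDD participants planned: 100 (Study Population).
- Attrition: 20% (Recruitment), with no split by reason.
- Gastrointestinal events: 21-32% (Side Effects).

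**Step 1: size of the set.** 100 × (1 − 0.20) = 80 completers and 20 dropouts.

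**Step 2: suicidality that leads to withdrawal.** Let k participants be withdrawn under item 4 before Week 8.
- All treated: k/100.
- Completers: 0/80 for every k, because none of the k has complete data.
- Exact upper 95% limit for 0/80: 1 − 0.025^(1/80) = 4.5%.
- k is not given. Assuming k = 1, 2, 3 or 5, the all-treated figure is 1%, 2%, 3% or 5%. For k = 3 the exact 95% CI is 0.6-8.5%.

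The completer result and its interval are the same in each case, so they carry no information about k. At k = 5 the observed all-treated rate of 5% lies above the completer upper limit of 4.5%.

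**Step 3: adverse events that lead to withdrawal.** The same argument gives 0/80 under item 5. If 10 of the 20 dropouts left for an adverse event (assumption; range 5-15), the all-treated rate is 10/100 = 10% (exact 95% CI 4.9-17.6%), with a range of 5-15%.

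**Step 4: common adverse events.** With N cases among 100 and c of them among the 20 dropouts, the completer rate is (N − c)/80.

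| Cases among the 20 dropouts (assumption) | N = 21 | N = 32 |
|---|---|---|
| Dropout unrelated to the event (c = 0.20 × N) | (21 − 4.2)/80 = 21% | (32 − 6.4)/80 = 32% |
| c = 10 | 11/80 = 13.8% | 22/80 = 27.5% |
| c = 20 (extreme) | 1/80 = 1.25% | 12/80 = 15.0% |

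The direction and size of any bias here depend on how many dropouts are cases. If dropout is unrelated to the event, no bias is expected.

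**The case against.** The strongest reply is that the defect is silence. The complete-data sentence sits in a plan about THINC-it performance, the objectives include no safety objective, and nothing says that adverse events will be tabulated on completers. This largely stands, and it limits the conclusion to what would follow if the stated set were used. It does not remove the point: the sentence is unqualified, no other set exists, and the C-SSRS is among the secondary measures to which the plan's analyses refer.

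A reader might infer more in four ways. The documents do not support any of them.
- *Withdrawn patients disappear from the record.* They do not. All adverse events are recorded, with any resulting discontinuation of the product, and serious events are reported. The gap is in planned analysis: the recording and reporting sections give no denominator and no summary.
- *Known harms would be reported as near zero.* No section says so. For gastrointestinal events, Step 4 comes close to zero only at the low end of the stated frequency and with all 20 dropouts being cases.
- *Completers can show no worsening on the C-SSRS.* They can. Withdrawal item 4 sets no score threshold, and ideation first seen at Week 8 occurs in a completer. The structural zero applies only to suicidality that triggered withdrawal. Likewise, Transition to Standard of Care allows a dose reduction or stopping the drug for side effects, so a treatment-limiting event need not mean leaving the study.
- *The C-SSRS range is cut at both ends.* Both rules act on high scores only.

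It is also fair to say that relating the C-SSRS to cognition is a deliberate choice by the sponsor. That use can remain.

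**Conclusion.** The point holds in a limited form. As written, participants withdrawn before Week 8 for suicide-ideation risk or a risky adverse event are outside every stated analysis, and the C-SSRS has no planned safety summary.

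If safety were summarised on the stated set, suicidality and adverse events leading to withdrawal would each be 0 of about 80, by construction. That result rests only on the withdrawal conditions, the complete-data rule and the 20% attrition figure. The all-treated comparisons (3% for suicidality, 10% for adverse event withdrawals) rest on assumed splits of the 20 dropouts and only illustrate the size. For common adverse events, understatement is possible but not established.

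This should be corrected before analysis. A stated rule selects participants on the outcome, which is more than missing detail, and the data needed to avoid it are already being collected.

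**What to change.** In the Statistical Plan:
1. State that the complete-data rule does not apply to safety.
2. Define a safety set of all MDD participants who took at least one dose of vortioxetine, using every visit attended.
3. On that set, summarise adverse events, serious adverse events, discontinuations by reason, and treatment-emergent or worsening C-SSRS ideation or behaviour at any post-baseline visit. Count withdrawals under items 4 and 5 as events, and give numbers, percentages and exact 95% CIs.
4. Keep the correlation of the C-SSRS with cognition if wanted, labelled exploratory.

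The cost is a paragraph of text and a few tables from visits already scheduled. The reported event rates may be less favourable. No eligibility, withdrawal or treatment rule changes.

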## **PROCEDURES FOR PARTICIPANTS WITH MAJOR DEPRESSIVE DISORDER**

### ***Visit 1 (Screening)***

The initial visit entails the provision of detailed study information to participant and obtainment

of informed written consent. A member of the research team will assess participants' eligibility based on inclusion/exclusion criteria and confirm a diagnosis of MDD with the M.I.N.I. 5.0 and the Structured Clinical Interview for DSM-5 (SCID) to assess for mixed features symptomatology. Demographics including date of birth, sex, and race will be recorded. Years of education will be recorded as well. Lifestyle factors (i.e. caffeine, exercise, alcohol, nicotine and marijuana ) will also be recorded. Psychiatric and medical history, number of psychotropic medications received according to participant self-report/clinical chart review, as well as anthropometrics (including height, weight and waist circumference) will be measured. Resting heart rate and blood pressure will also be measured. Participants will be evaluated with the MADRS by a member of the research team trained in MADRS scoring to assure the severity threshold is indicative of non-remission (MADRS  $\geq$  20). The Columbia Suicide Severity Rating Scale (CSSRS) will also be used as part of participant assessment. In addition, participants will be asked to report any experience of adverse event(s) prior to study enrollment. Participants will be asked to complete the NART to estimate premorbid intelligence quotient (IQ). Upon confirmation of study eligibility, the participant will be scheduled for future appointments.

### ***Visit 2 (Day 0: Week 0; Baseline)***

Participant will be asked to report any adverse event(s) or any changes to medications. The Clinical Global Impression – Severity (CGI-S), MADRS, as well as the CSSRS scales will be used as part of participant assessment. Anthropometrics (including weight and waist circumference), resting heart rate and blood pressure will be measured. History of caffeine, alcohol, nicotine, exercise and marijuana use will be recorded as well. Participants will be provided with an opportunity to work through the modified THINC-it to minimize potential practice effects with a research team member. This will allow the participant with an opportunity to ask any outstanding questions. The THINC-it tool will be administered via tablet to evaluate objective and subjective measures of cognitive function. THINC-it tests will be consistently delivered in the following order: Spotter, Symbol Check, Codebreaker, Trails, and PDQ-5-D to all participants with a member of the research team instructing participants to read the tutorial

instructions preceding each of the THINC-it tasks. Participants will complete the pen-and-paper version of the Digit Symbol Substitution Test (DSST) and the Trail Making Test B (TMT-B).

Participants will also complete all secondary self-report assessments using paper-based scales/questionnaires and consist of the following scales: Endicott Workplace Productivity Scale (EWPS), Sheehan Disability Scale (SDS), Wellbeing Index (WHO-5), Snaith-Hamilton Pleasure Scale (SHAPS), Generalized Anxiety Disorder (GAD-7), Perceived Deficits Questionnaire for Depression (PDQ-5-D), International Physical Activity Questionnaire (IPAQ), 36-Item Short Form Survey Instrument (SF-36), Insomnia Severity Index (ISI), Pittsburgh Sleep Quality Index (PSQI), Epworth Sleepiness Scale (ESS) and THINC-it satisfaction questionnaire. All self reports will be administered by a member. All study procedures will take place in a quiet setting. Fasting (12-hours) clinical and research bloodwork will also be collected.

Participants will receive vortioxetine 10-20 mg (flexibly dosed) over the course of 8 weeks and to be taken once daily with the option to increase to vortioxetine 20 mg/day following visit 3 of the treatment based on clinical discretion (e.g. efficacy and tolerability). This dose was chosen based on extant evidence demonstrating improvements in cognitive function (i.e., executive function, attention/speed of processing, and memory), independent of improvement in depressive symptoms, over an 8-week period [19, 20]. Participants will be asked to store the medication at room temperature (i.e., 15-30 °C).

All participants will be fully informed of safety and tolerability concerns related to the treatment and will be instructed to report any treatment emergent adverse events (TEAEs) of concern to a member of the research team. Moreover, members of the research team will specifically probe and monitor all participants regarding side-effects at each visit. Participants will also be provided with a cell phone number accessible 24 hours a day, seven days a week. The cell phone will be carried on a rotating basis by individual members of the research team.

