***Inclusion Criteria for Participants with MDD:***

1. The participant is able and willing to provide informed consent.
2. The participant is male or female 18-65 years of age.
3. The participant has received a current diagnosis of a major depressive episode (MDE) as part of MDD as per DSM-5 criteria.
4. The participant's current MDE is confirmed by the Mini International Neuropsychiatric Interview (M.I.N.I 5.0.).
5. The participant is an outpatient of a psychiatric setting.
6. The participant has a MADRS score  $\geq 20$  at screening and baseline.
7. At least one prior MDE formally diagnosed by a healthcare provider or validated by previous treatment (e.g., guideline-informed pharmacotherapy and/or manual-based psychotherapy).

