## **Transition to Enrollment**

Patient will discontinue only antidepressants. Patients' existing antidepressant dosage will be decreased gradually over a course 10-14 days. At the same time, participants will be started on 10mg of Vortioxetine. It takes about 10-14 days for Vortioxetine to achieve steady states. For patients who are already taking antidepressants at the start of study, if they are abruptly discontinued, they are at risk for discontinuation syndrome. Therefore, both drugs will be co-prescribed for about 10-14 days and then the index antidepressant will be discontinued.

Serotonin syndrome or other additive side effects is very unlikely to be a concern. Should the patient's physician determine another optimal schedule, this will be followed instead. All MDD participants will be supervised by [name], prior to enrollment of the study. All patients will be monitored by a psychiatrist during the study. Furthermore, patients will have access to a 24-hour study number where they can contact research staff anytime, should they experience any adverse events. Therefore, there will always be an open line of communication between patients and the research staff.

The above mentioned procedures will only be carried out once participants have consented to take part in the research and signed the informed consent form.

Patients will be seen by a clinician on a biweekly basis for the antidepressant washout period. Clinician will be assessing the patient on adverse side effects, as well as mood.

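### No pregnancy test is named at any MDD visit, so vortioxetine can be started in a patient with an unrecognised pregnancy although pregnancy is an exclusion

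*Combined protocol and SAP*

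**What the plan says.** **Who may enter.** Inclusion criterion 2 for MDD participants reads "The participant is male or female 18-65 years of age". The exclusions include "13. Pregnant and/or breastfeeding", "23. Hyponatremia" and "24. Moderate hepatic impairment". None of these three comes with a test or a threshold. Conditions for Withdrawal from the Study lists becoming pregnant as a reason to stop.

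**When eligibility is settled.** At Visit 1 a research team member works from diagnostic interviews, history, chart review, rating scales and vital signs; no laboratory test is listed. That section ends: "Upon confirmation of study eligibility, the participant will be scheduled for future appointments". In the MDD Patient Summary Chart the inclusion/exclusion row is ticked at Screening only. One criterion, the MADRS threshold, is to be met "at screening and baseline".

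**What happens at Week 0.** The Visit 2 text says "Fasting (12-hours) clinical and research bloodwork will also be collected" and goes on to the supply of vortioxetine, with no condition on results. The chart ticks bloodwork, vortioxetine treatment, dispensing and a physician visit in that same column. Study Medication: Vortioxetine starts 10 mg daily on day 1.

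**Patients already on an antidepressant.** Transition to Enrollment sets a default taper of 10-14 days and adds: "At the same time, participants will be started on 10mg of Vortioxetine".

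**The concern.** Excluding pregnancy protects a patient only if some step can reveal a pregnancy she does not know about. Medical history finds known pregnancies. Visit 2 asks about adverse events and medication changes, and Recordings of Adverse Events says that pregnancy in itself is not an adverse event, so that question does not by itself lead to pregnancy status. With no test named, drug exposure can begin in someone the protocol means to keep out, and nobody will have departed from the schedule.

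What is at stake is participant safety and the application of a stated exclusion. Nothing here bears on the sample size, the estimates or the tests in the Statistical Plan.

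A related but weaker question concerns hyponatremia and moderate hepatic impairment. The only pre-treatment blood sample is drawn at the visit where drug is dispensed, and no step says that its results are read first.

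**Working it through.** There is no figure in the plan to reproduce. The check sets the sections side by side and counts the chart.

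1. **Pregnancy tests in the visit texts.** Visits 1 to 5 for MDD participants were read in full. Visits naming a pregnancy test: 0 of 5.
2. **Pregnancy tests in the chart.** The MDD Patient Summary Chart has 36 rows. Rows naming a pregnancy test: 0 of 36. The schedule is detailed (it lists waist circumference and a satisfaction questionnaire), so a planned test would be expected to appear.
3. **Blood before dispensing.** The bloodwork row is ticked at Week 0 and Week 8. Dispensing is ticked at Week 0, Week 2 and Week 4. Bloodwork ticks in a column before the first dispensing column: 0.
4. **Content of the blood panel.** The clinical part is not itemised. The only analytes named, under Secondary Assessment Instruments, are BDNF, cytokines and insulin, as examples of biomarker outcomes. Sodium, liver tests or a serum pregnancy test may be in the panel; the documents do not say.
5. **Condition on dispensing.** No sentence in Visit 2, Transition to Enrollment or Study Medication makes supply depend on a result. Visit 2 is Day 0 and dosing starts on day 1, which leaves room to read a Day 0 result before the first dose but does not require it.
6. **Resulting sequence.** Eligibility is confirmed at Visit 1 without laboratory tests; at Week 0 blood is drawn and drug dispensed; the first dose is on day 1; the next scheduled blood is at Week 8. No pregnancy result has to exist at any point before the first dose.
7. **Size of the remedy.** One test per woman who could be pregnant, among 100 planned MDD patients: between 0 and 100 × 1 = 100 tests. The share of women is not given, so 100 is only a ceiling.

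**The case against.** **Supervision exists.** Transition to Enrollment provides supervision of every MDD participant before enrollment and psychiatrist monitoring during the study, and the chart has a physician visit at Week 0. This stands as a partial safeguard and makes the fix easy to place. It requires neither a pregnancy test nor the reading of a result.

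**The clinical panel may already contain the tests.** That is possible. Even so, nothing requires a serum pregnancy result to be read before dispensing.

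**The consent form may mention a test.** Consent pages are not part of the text reviewed, and the protocol says that some patient procedures are also set out there. The point is therefore confined to the visit descriptions and the chart, which are present.

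**The laboratory exclusions may mean known conditions.** This largely stands. Hyponatremia and moderate hepatic impairment sit among items that read like label warnings, have no thresholds, and can be answered from the history taken at screening. A reader might infer that the plan commits to screening for undiagnosed cases and fails to do it. The documents do not support that.

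**A delay of up to 14 days.** A reader might take the gap from the Week 0 draw to the Week 2 visit as the time before results are read. No review time is documented, and clinician contact during the washout may come sooner, so no such range is claimed. The harm of losing an existing antidepressant would reach only patients taking one, a number not given, and the physician may set another schedule.

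**The baseline tick.** The MADRS row is already ticked at Week 0, so that criterion is not left unmeasured. This stands; the extra tick is useful as the place where the pregnancy result is acted on.

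**A single Week 0 test misses later pregnancies.** True. The point here concerns starting treatment.

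**Conclusion.** The pregnancy point holds, with high confidence: no MDD visit or chart row names a test, and vortioxetine is dispensed at Week 0 without any result being required. The schedule governs all 100 planned MDD patients. How many would have an unrecognised pregnancy is not estimated, because the documents supply no prevalence and no sex split. The conclusion assumes that a site does what the visit texts and chart say and no more; a site that tests routinely would close the gap by its own practice.

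The laboratory part is secondary and held with lower confidence. It matters only if the Week 0 clinical panel is intended to apply the hyponatremia and moderate hepatic impairment exclusions. No claim is made that a low baseline sodium raises the risk on treatment.

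Overall this should be fixed, as a cheap improvement in participant safety.

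**What to change.** **Main change.** In the Visit 2 text and the MDD Patient Summary Chart:

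- Add a rapid pregnancy test at Week 0 for women who could be pregnant, with the result read before vortioxetine is dispensed.
- Add an inclusion/exclusion tick at Week 0, ahead of dispensing, so that the result is applied as an eligibility check. The physician visit already charted there is a natural place for it.

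The cost is a short amendment and at most 100 inexpensive tests.

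**Optional.** If the Week 0 clinical panel is meant to apply the hyponatremia and moderate hepatic impairment exclusions, say so, and have the Week 0 physician review the results before the first dose and before any antidepressant taper begins. No extra blood draw is proposed. The downside is that the first dose may move later if results are not back by day 1; the laboratory turnaround is not given. Clinical thresholds are for the sponsor to set.
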